#### 12.4.1.2. Secondary Treatment Effect Parameters

The VIth International Workshop specifies a number of outcome metrics related to time [1] (see [Section 16.3](#)). The following parameters are considered most relevant to this time-limited study and will be analyzed both globally across all cohorts and by dose level.

- Distribution of response categories by treatment group and overall.
- Time to progression – Time from the initiation of treatment to disease progression with deaths due to unrelated causes censored.
- Progression-free survival – Time from the initiation of treatment to disease progression or death from any cause.
- Time to best observed response – Time from the initiation of treatment to best observed category of response.

- Percent and absolute change in quantitative serum levels of monoclonal and total IgM.

Kaplan-Meier analyses will be used to analyze time to event data. Analysis of IgM data will be performed using a repeated measures mixed model. MyD88 L265P mutation status will be used as a covariate in statistical analyses.

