### **1.3. Study Design and Methodology**

#### ***1.3.1. Brief Background and Rationale***

IMO-8400 is a second-generation oligonucleotide antagonist of Toll-like receptors (TLR) 7, 8, and 9, which blocks immune activation mediated through those receptors. In a Phase 1 study IMO-8400 was administered to healthy adults by SC injection at single-doses and multiple-doses (once weekly for 4 weeks) up to 0.6 mg/kg (see [Section 4.4](#) for details). All treatments were well-tolerated, with mild injection site reactions (ISRs) and no pattern of systemic reactions or laboratory changes.

In recent studies, a high frequency of mutation in the signaling pathway downstream of TLR7, 8, and 9 has been identified in patients with B-cell malignancies, including more than 90% of patients with WM [\[2\]](#). In vitro studies of B-cell tumor lines indicate that such mutations are associated with an increase in cell activation, proliferation, and survival [\[3\]](#), and that loss of endosomal TLRs results in markedly decreased cell proliferation and survival [\[4\]](#). Data from Idera indicate that treatment of such cell lines with IMO-8400 has a similar effect (see Investigator's Brochure for details).

The current study represents the first clinical trial of IMO-8400 in patients with B-cell malignancy.

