 Bone marrow biopsy and aspirate will be collected at Screening, EOT, and to document complete response as appropriate (see [Section 16.2](#)) and submitted to central laboratory (see [Section 9.4.4](#) and [Section 12.4.1](#)). If patients have a bone marrow biopsy within 4 weeks of EOT, the biopsy will not be repeated at EOT. The Screening Visit sample will also be assayed for the MyD88 L265P mutation.

 Assessment of all prior injection site(s) with grading and measurement of any reaction (see [Section 9.6.5](#)). In addition, on dosing days, the planned injection site will be assessed to confirm it is appropriate for use.

 Schedule applies to all patients receiving once weekly dosing and to the first weekly dose for all patients receiving twice weekly dosing (see [Section 1.3.2](#) and [Section 8.4](#) for details).

 Response assessment is summarized in [Section 16.2](#) and includes total serum IgM, serum monoclonal IgM, bone marrow histology, adenopathy/organomegaly, cytopenias, and symptoms (see [Section 9.5](#) for details). Total IgM and monoclonal protein lab tests (see Section 9.4.2 for details) will be submitted to central laboratory.

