**Figure-1. TLR and BCR Signaling Pathways in B-cells**

A central feature of malignant cell transformation is the development of dysregulated or autonomous cell activation resulting in increased cell proliferation and survival. This can be the result of specific ‘oncogene’ mutations or defects in the control of the expression of critical genes. Studies of B-cell malignancies have identified changes in the BCR signaling pathway, and more recently in the TLR signaling pathway, that drive NF-κB expression and the malignant phenotype. These changes include:

- Mutations in BCR pathway genes, including CD79A/B and CARD11 [3].
- Increased expression of myeloid differentiation primary response gene (88) (MyD88), the adapter (linker) protein that binds to TLRs [14].
- Mutations in MyD88 [15].

The most common alteration identified to date in MyD88 is the L265P mutation. Table-6 displays the frequency of MyD88 L265P among B-cell malignancies and proliferative diseases. The mutation is present in over 90% of WM, in ~30% of Activated B-cell-like Diffuse Large B-cell Lymphoma, and at lower frequencies in other, more common lymphomas.

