**Table-6. Incidence of MyD88 L265P mutation in selected B-cell malignancies**

Disease	Incidence of Disease (SEER 2001)	% Patients with MYD88 L265P mutation	Estimated Incidence 2013 a (New cases/year)	Reference for MyD88 frequency
ABC-DLBCL	6,789 b	29%	2,150	[16]
Waldenström's macroglobulinemia	1,144	91%	1,200	[2]
Chronic Lymphocytic Leukemia	16,984	3%, 7%	925	[17,18]
Primary CNS Lymphoma	1,200	36%, 38%	480	[19,20]
Marginal Zone Lymphoma c	3,247	9%, 4%	225	[16,21]

Abbreviations: ABC-DLBCL=Activated B-cell (type) Diffuse Large B-cell Lymphoma; CNS=central nervous system; DLBCL=Diffuse Large B-cell Lymphoma; MyD88=Myeloid differentiation primary response gene (88); SEER=Surveillance Epidemiology and End Results

a. New cases/year are adjusted + 10% due to population growth since data collection [22,23]

b. Incidence of DLBCL, 24,246; ABC-type represents 28% of all DLBCL.

c. Marginal Zone Lymphoma is also referred to as MALT, Mucosa-Associated Lymphoid Tissue Lymphoma

Recent in vitro studies of B-cell tumor lines with L265P mutation suggest that increased TLR signaling contributes to the malignant phenotype of these cells [4]. Specifically, cell proliferation and survival decreased markedly under the following conditions:

- Impaired expression of endosomal TLRs, using an inhibitory RNA.
- Enzymatic elimination of endogenous nucleic acids in the culture supernatant.

Idera Pharmaceuticals, Inc. has conducted independent studies using B-cell tumor lines, including LY10, a cell line with the L265P mutation and increased MyD88 expression. LY10 cells cultured in vitro with IMO-8400 demonstrated decreased growth and survival (see Investigator Brochure for details). Severe combined immunodeficient mice inoculated with LY10 developed progressive disease and died. Treatment with IMO-8400 prolonged median survival from 33 to 48 days (see Investigator's Brochure for details).

Taken together, these data directly support the hypothesis that an antagonist of TLR7, 8, and 9 would have a therapeutic effect in patients with B-cell malignancies, particularly those characterized by MyD88 L265P mutation or increased MyD88 expression.

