### 5.3. Exploratory Objectives

- To investigate associations between the treatment effect of IMO-8400 and selected biomarkers (e.g., serum cytokines).
- To correlate the presence of MyD88 L265P mutation with clinical outcome.
- To assess the potential immunogenicity of IMO-8400 administered by SC injection.

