## **6.7. Maximum Number of Patients and Maximum Exposures**

The maximum exposures to IMO-8400, the investigational agent in this study, will be as follows:

- Maximum number of patients: Approximately 60 patients in planned escalation and expansion cohorts; potential for additional patients in contingency cohorts or as replacements.
- Maximum dose level: Undefined (pending dose escalation results). The planned dose escalation cohort levels for IMO-8400 are 0.6, 1.2, 2.4, and 3.6 mg/kg administered once weekly and 1.2 mg/kg administered twice weekly
- Maximum duration of exposure: undefined (treatment is until study completion or until the patient experiences intolerable toxicity, disease progression, or withdraws consent, whichever comes first as defined in [Section 6.10.2.2](#)).

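### MyD88 L265P status, about 91% positive by the protocol's own figure, is fixed as a covariate without limit, although within dose level it will usually be constant or rest on one or two patients

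*Protocol*

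**What the plan says.** Section 12.4.1.2 lists the secondary treatment effect parameters: response categories, time to progression, progression-free survival, time to best response, and percent and absolute change in monoclonal and total IgM. They are to be analysed over all cohorts together and also within dose level. Time-to-event data go to Kaplan-Meier analysis. For IgM, "Analysis of IgM data will be performed using a repeated measures mixed model". The section closes with "MyD88 L265P mutation status will be used as a covariate in statistical analyses". Section 12 names no other covariate. It sets no limit on this one by dose level, endpoint or number of wild-type patients.

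On how common the mutation is, Section 4.2 says "The mutation is present in over 90% of WM", and the Table-6 column for "Patients with MYD88 L265P mutation" gives 91% for this disease. Status comes from the screening marrow ("The Screening Visit sample will also be assayed for the MyD88 L265P mutation", footnote to the schedule of events) and is not an eligibility criterion in Section 1.5. It also serves an exploratory objective in Section 5.3, "To correlate the presence of MyD88 L265P mutation with clinical outcome", and Section 12.5 lists it as an exploratory factor.

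The analysis sets are small: escalation cohorts of 3 to 6 (Section 6.2), up to 22 more patients at the MTD or RP2D (Section 12.1), and in total "Approximately 60 patients in planned escalation and expansion cohorts" (Section 6.7).

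**The concern.** A covariate helps only if it varies among the patients analysed. If about nine in ten patients share one value, a cohort of 3 to 6 will often hold no patient with the other value, and a model for that cohort then cannot estimate the term. Where a single wild-type patient is present, the estimated mutation effect is that patient's result set against everyone else's.

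Followed literally, the sentence would produce by-dose models that drop the term in some cohorts and not in others, and adjusted estimates that depend on one or two people. Dose levels would then be compared on different footings.

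A related point concerns the IgM model. IgM is measured at screening and throughout treatment (Sections 9.4 and 9.4.2), and entry requires at least 0.5 g/dL of monoclonal IgM with no upper limit (Section 1.5.1). Starting level is thus an available and natural adjustment variable for IgM change, yet the only covariate the protocol names is the nearly constant one.

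**Working it through.** **Inputs from the protocol.** Prevalence of L265P p = 0.91 (Table-6); cohort sizes 3 to 6; expansion n = 22; total about 60. Since the text says over 90%, results are also shown at 0.90 and, as an assumption, at 0.95.

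**The plan's own figures.** For n = 22, the chance of seeing an adverse event with a 10% rate is 1 − 0.9^22 = 0.90, as stated. The one-sided exact test of 33% against 10% rejects at 6 or more responses (alpha 0.018) with power 0.784, or 0.794 if one third is used, consistent with the stated 79%. Neither figure involves the covariate.

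**Number of wild-type patients.** Expected number = n(1 − p). P(none) = p^n. P(at most one) = p^n + n(1 − p)p^(n−1).

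| n | Expected wild-type (p = 0.91) | P(none), p = 0.91 | P(none), p = 0.90 | P(none), p = 0.95 |
|---|---|---|---|---|
| 3 | 0.27 | 75% | 73% | 86% |
| 6 | 0.54 | 57% | 53% | 74% |
| 22 | 1.98 | 12.6% | 9.8% | 32% |
| 60 | 5.4 | 0.3% | 0.2% | 4.6% |

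At n = 22 and p = 0.91, P(at most one) = 0.126 + 22 × 0.09 × 0.91^21 = 0.40, and P(at most two) = 0.68. If 6 escalation patients at the same dose are added, n = 28: expected 28 × 0.09 = 2.5, P(none) = 0.91^28 = 7%.

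**All dose levels at once.** Assume the favourable case of five levels with 6 patients each, one of them expanded by 22. The chance that every level contains both mutation groups is (1 − 0.91^6)^4 × (1 − 0.91^28) = 0.432^4 × 0.929 = 3.2%. At p = 0.90 it is 4.6%, and at 0.95 it is 0.4%. So with at least 95% probability the covariate is constant in at least one dose level.

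**Precision where it can be estimated.** The variance of the indicator is 0.91 × 0.09 = 0.082, against 0.25 for an even split, so the standard error of its effect is √(0.25/0.082) = 1.75 times larger. The difference between the groups detectable with 80% power (two-sided 0.05, one measurement per patient, normal approximation) is (1.96 + 0.84) × √(1/w + 1/m) SD, for w wild-type and m mutated patients:

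- 2 versus 20: 2.80 × 0.742 = 2.1 SD.
- 5 versus 55: 2.80 × 0.467 = 1.3 SD.

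**Adjusting for baseline IgM.** The protocol gives no IgM variance or correlation. With equal variances σ² and correlation ρ, unadjusted change has variance 2σ²(1 − ρ), and change adjusted for baseline has σ²(1 − ρ²). The ratio is (1 + ρ)/2: 0.65, 0.75, 0.85 and 0.95 for ρ = 0.3, 0.5, 0.7 and 0.9. That is a reduction of 35% down to 5%.

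**What MyD88 status itself might explain.** For a wild-type versus mutated difference of d within-group SD, the share of variance is 0.082d²/(1 + 0.082d²): about 2%, 8% and 16% for d = 0.5, 1.0 and 1.5 (assumed values).

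**The case against.** Several parts of the case on the other side are sound.

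- *Baseline IgM.* A reader might infer that the plan leaves baseline IgM out of the analysis. The protocol does not say so. Baseline is the reference for the change endpoints and for the response categories in Section 16.2. No fixed effects of the mixed model are listed at all, and Section 12 leaves further methods to the SAP. Silence is not exclusion, so this part is a recommendation and not an error in the protocol.
- *Reason for naming the mutation.* The drug affected L265P tumour lines but not a wild-type xenograft (Section 4.4), and correlating status with outcome is a stated objective. It would be wrong to say that status should not be examined, or that it must explain almost no variance: under the assumed effects above it could explain 2% to 16%.
- *Pooled analysis.* Section 12.4.1.2 also requires a global analysis. With about 60 patients, roughly 3 to 6 wild-type patients are expected (p = 0.95 to 0.90), so the term is usually estimable there.
- *Kaplan-Meier.* A reader might infer a contradiction because Kaplan-Meier estimation takes no regression covariate. Curves can be drawn by status, so the sentence can be met that way.
- *Meaning of by dose level.* One model with dose as a factor and a common mutation term avoids separate fits. Even then, only dose levels with both groups inform the term, and the protocol does not say that this is meant.

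The 91% is also a literature rate, not the rate among enrolled patients. None of this rescues an unrestricted covariate in analyses of 3 to 6 patients.

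**Conclusion.** The point holds for by-dose-level analyses. At 91% positive, status does not vary at all in 57% to 75% of cohorts of 3 to 6. In an expansion group of 22 it rests on at most two wild-type patients in about two trials out of three. The conclusion does not change over 90% to 95% prevalence. It assumes that patients enrol at roughly the literature rate, which is reasonable because mutation status plays no part in eligibility.

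In the pooled analysis the term is weak, not impossible: with about 5 wild-type patients, only a difference of around 1.3 SD would be found reliably. The benefit of baseline IgM is real in direction but of unknown size, between 5% and 35% of the variance of change under the stated assumptions. It applies most directly to absolute or log-scale change, since percent change already scales to the starting level.

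The primary safety objective, the objective response test, and the stated power and sample size are untouched.

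**What to change.** Replace the closing sentence of Section 12.4.1.2 with a limited rule, and carry it into the SAP:

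1. MyD88 L265P status is examined only in analyses pooled over dose levels: response rates by status with exact intervals, Kaplan-Meier curves by status shown descriptively, and at most an exploratory term in the pooled IgM model. It is not a covariate in by-dose-level analyses.
2. The repeated measures mixed model for IgM change includes baseline IgM (for example on the log scale), dose level and visit.

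The cost is a change of wording. Mutation status and baseline IgM are already collected, and no procedure or patient number changes. What is given up is an adjusted MyD88 effect within each dose level, which the data could rarely supply. The exploratory objective in Section 5.3 is still served by the pooled analyses and by Section 12.5.

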## **12.5. Exploratory Analyses**

The following investigational factors will be analyzed with regard to disease status:

- Presence or absence of MyD88 L265P mutation in tumor cells.
- Serum cytokine levels.
- Serum levels of antibody to IMO-8400.
- NF- $\kappa$ B inhibition.

## **12.6. Identification of Study Event Days and Times**

Study events will be recorded using the calendar date and (where applicable) the time to the nearest minute.

For purposes of post-study analysis (e.g., tables and listings), study days will be designated as follows:

- Day 1 is defined as the calendar day of the first injection of study drug.
- The days prior to Day 1 are designated Day -1, Day -2, etc; there is no Day 0.
- The days following the day of the first injection of study drug are designated Day 2, Day 3, etc.
- The day of the last injection of study drug is indicated by adding the suffix "L," e.g., if the last injection is administered on Day 43, it will be displayed as "Day 43L."
- The days following the last injection of study drug are designated Day 1P, Day 2P, etc.

The times of events related to dosing of study drug will be designated as minutes or hours before or after the time of dosing (i.e., the SC injection of study drug), which is designated as  $t = 0$  (zero). Thus, 15 minutes prior to dosing is  $t = -15$  min; 2 hour after dosing is designated  $t = 2$  h.

## **12.7. Handling Missing Data**

Missing data will not be imputed. In time-to-event analyses using Kaplan-Meier methodology, patients who do not experience the event of interest will be censored. Rules for censoring of data will be described in the SAP. Further details for handling of missing, duplicated or unscheduled data will be given in the SAP.

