### 12.1. Sample Size Determination and Study Power

Following identification of the MTD/RP2D, up to an additional 22 patients will be enrolled at the MTD or proposed RP2D level. With a total sample size of 22 patients, there is a 90% probability to detect an AE with a true incidence rate of 10%. A secondary objective of this study is to determine the treatment effect of IMO-8400 in patients enrolled at the MTD/RP2D. Using the exact binomial distribution with a 1-sided test and an alpha of 0.05, there is 79% power to detect a response rate of 33% as compared to a null response rate of 10%.

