#### 12.4.1.1. Primary Treatment Effect Parameter

The primary treatment effect parameter is objective response rate, defined as the occurrence of CR, VGPR, PR, or MR.

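### Kaplan-Meier with all non-event patients censored is a poor estimator for time to best observed response: if censoring falls at death or treatment-ending progression, it overstates the proportion responding

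*Protocol*

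**What the plan says.** Section 12.4.1.2 lists the secondary treatment effect parameters, to be analysed across all cohorts and by dose level. One is time to best observed response, defined as "Time from the initiation of treatment to best observed category of response". Time to progression and progression-free survival are in the same list. One estimator is then named for all of them: "Kaplan-Meier analyses will be used to analyze time to event data". Response timing is not excepted.

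Section 12.7 says that in these analyses "patients who do not experience the event of interest will be censored", whatever the reason the event did not occur. The next sentence adds: "Rules for censoring of data will be described in the SAP".

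The proportion responding is reported separately. Section 12.4.1.1 states: "The primary treatment effect parameter is objective response rate, defined as the occurrence of CR, VGPR, PR, or MR".

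**The concern.** Censoring assumes that a patient who leaves the risk set has the same future chance of the event as those who stay. For progression-free survival, progression and death are themselves the event, so the problem does not arise. For response timing they are not. A patient who dies without responding cannot respond, and one who progresses and stops treatment has, for practical purposes, lost the chance to respond to study drug. Censoring these patients when that happens passes their share of probability to the patients who remain, and the curve rises too far.

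The protocol makes censoring near progression the natural outcome. Under Sections 1.7.3 and 6.10.2.2, continued 12-weekly assessment applies only to patients who stop for reasons other than progression. Beyond the end-of-treatment and end-of-study visits, a patient who stops for progression has no further scheduled response assessment. The definitions of time to progression and progression-free survival both say how deaths are handled; the definition of time to best observed response does not.

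At stake is how the response-timing curve is read, overall and by dose level. It could show a higher proportion responding than the objective response rate from the same patients, by an amount that depends on how many progressed.

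**Working it through.** **1. The plan's own figures.** Section 12.1 gives no figure for response timing. It does give a sample size of 22 and 79% power for a 33% response rate against a null of 10%, "Using the exact binomial distribution with a 1-sided test and an alpha of 0.05". Requiring at least 5 responses of 22 gives a type I error of 0.062, which is too high. Requiring at least 6 gives 0.018, with power 0.784 at 33% and 0.794 at one third. The 79% is reproduced. I take 33% and n = 22 from here as the illustrative response proportion and group size.

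**2. Input the protocol does not give.** Let c be the share of patients who, by the horizon, die or progress off treatment without responding. This is an assumption, varied from 0% to 60%. All other patients are assumed to be followed to the horizon.

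**3. Formula.** With p = 0.33 and constant cause-specific hazards:
- total cumulative hazard H = −ln(1 − p − c);
- response part H1 = [p/(p + c)] × H;
- one minus Kaplan-Meier, censoring at the competing event, = 1 − exp(−H1);
- cumulative incidence of response = [p/(p + c)] × [1 − exp(−H)] = p.

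For c = 0.40: H = −ln(0.27) = 1.309, H1 = (0.33/0.73) × 1.309 = 0.592, and 1 − exp(−0.592) = 0.447.

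| c (assumed) | 1 − Kaplan-Meier | Cumulative incidence | Excess (points) |
|---|---|---|---|
| 0% | 0.330 | 0.330 | 0 |
| 10% | 0.350 | 0.330 | 2.0 |
| 20% | 0.375 | 0.330 | 4.5 |
| 30% | 0.406 | 0.330 | 7.6 |
| 40% | 0.447 | 0.330 | 11.7 |
| 50% | 0.506 | 0.330 | 17.6 |
| 60% | 0.611 | 0.330 | 28.1 |

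Simulation (4,000 runs of 22 patients) gives means of 0.377, 0.445 and 0.604 for c of 20%, 40% and 60%, against a true 0.33.

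**4. A 22-patient example (constructed).** Seven patients respond, at weeks 4, 8, 8, 12, 16, 20 and 24 from the start of treatment. Eight progress without response, four at week 8 and four at week 16. Seven are event-free at week 24.
- Censored at progression: (21/22)(19/21)(14/15)(13/14)(8/9)(7/8) = 0.582, so one minus Kaplan-Meier is 41.8%.
- Non-responders carried to week 24: the product reduces to 15/22, giving 31.8% = 7/22.

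With four progressors (two at each time) the first figure is 35.5%. With twelve (six at each time) it is 56.2%. The second stays at 31.8%. In the twelve-progressor case the curve passes 50% at week 24, so a median time would be quoted for a group in which 7 of 22 responded.

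**5. What the comparison shows.** The patients and responses are the same in both calculations; only the censoring date differs. That date decides whether there is any overstatement.

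**The case against.** The strongest reply is that the protocol does not fix the error. Section 12.7 leaves the censoring rules to the SAP, which is not at hand. Carrying non-responders to the end of follow-up is compatible with the protocol's wording and removes the excess, as step 4 shows. Analysing responders only would also avoid it. This stands: the overstatement is a risk under the likely default. It does not remove the point, because the protocol itself chooses the estimator and the decision to censor. A method that is right only under one unstated censoring convention is a weak choice when a better one is available.

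Second, progression is not always terminal. Section 6.5.1 allows some patients to be treated past progression because response signs may be delayed, and Section 16.2 requires confirmation of progression by IgM. This also stands, and it limits which progressions should count as competing events.

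Third, a reader might infer that the stated response rate or the choice of dose is biased. The documents do not support that. The objective response rate is a separate binary measure, and the power statement rests on an exact binomial test of a response rate. The maximum tolerated dose is set by dose-limiting toxicities (Section 6.3.2), and no rule for the recommended Phase 2 dose uses this curve. Section 6.10.2.1 cites faster response at the highest dose studied, but as an interim observation. With 3 to 6 patients initially per escalation cohort, by-dose curves are imprecise anyway.

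Finally, the magnitudes rest on assumed event rates. That is correct, and is why a range is given.

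**Conclusion.** The point holds in conditional form. Kaplan-Meier with all non-event patients censored suits progression-free survival and time to progression, but not time to best observed response. If patients are censored at death or at treatment-ending progression without response, one minus Kaplan-Meier overstates the proportion responding by about 2 to 28 points. This assumes a true response of 33%, competing events in 10% to 60% of patients, constant hazards and otherwise complete follow-up. If non-responders are carried to the end of follow-up, or only responders are summarised, the excess is zero.

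A reader might infer that the curve is certain to exceed the objective response rate. That goes too far, because the censoring date is left to the SAP. The event also needs defining: as worded, best observed category is not limited to minor response or better, so a patient whose best category is stable disease could be counted as having the event.

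**What to change.** In Sections 12.4.1.2 and 12.7, and in the SAP:
- Keep Kaplan-Meier for progression-free survival and time to progression.
- For response timing, define the event as reaching the patient's best category, provided it is minor response or better. Estimate it by cumulative incidence (Aalen-Johansen).
- Count as competing events, when they occur without response: death, start of another anti-WM therapy, and progression that ends study treatment. Patients treated past progression stay at risk.
- Censor at the last assessment those still under assessment at the data cut, and those lost to follow-up or withdrawn without a competing event.

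Alternatively, summarise time to best response descriptively among responders and present it beside the objective response rate.

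The cost is analysis wording and programming; no new data are needed. The downside is that the reported proportion responding by a given time will be lower than a curve that censors at progression would show.
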